Helmet CPAP for Infants and Pediatric Patients with Acute Respiratory Distress

NCT04764929

Principal Investigator: [name]

August 23, 2021

Background

Study Purpose and Rationale:

Continuous positive airway pressure (CPAP) has become standard of care in pediatric patients with acute lung infections such as bronchiolitis and pneumonia. CPAP is currently delivered with several different patient interfaces: facemask, nasal mask and nasal prongs. In order for CPAP to be most effective there should be very little leak between the patient and the interface. This can be challenging in young pediatric patients as they are often not as compliant as adults with maintaining their interfaces in place. Leaks with the use of traditional CPAP interfaces may decrease effective delivered pressures also increase the risk of aerosolization of viral particles. Thus, an ideal interface would be one that forms a complete seal and is well tolerated. The use of a helmet interface to deliver CPAP could offer an effective alternative to traditional nasal or facemask CPAP interfaces and more consistently provide the prescribed pressure and decrease the chance of aerosolizing viral particles. Thus, we propose a pilot study to determine tolerability of helmet CPAP in children one month to five years of age with acute respiratory distress admitted to the pediatric ICU (PICU). A prior randomized controlled trial in the United States demonstrated helmet CPAP significantly decreases the intubation rate (18.2% versus 61.5%) compared to face mask CPAP in 83 adults with acute respiratory distress syndrome (ARDS).¹ The rate of adverse events were similar with three interface-related skin ulcers in each group: 6.8% in the helmet group had neck ulcers and 7.6% in the face mask group had nose ulcers. By achieving a complete seal with the use of a helmet CPAP, constant pressures can be delivered to the patient compared to air leaks often seen with traditional interfaces such as a full facemask or nasal mask. In a multicenter randomized controlled trial in Italy, 30 infants (children under one year of age) with respiratory syncytial virus (RSV) acute respiratory failure were randomized to receive CPAP by helmet (n = 17) or facial mask (n = 13).² Helmet CPAP had a lower treatment failure rate due to intolerance (17% vs 54%, P = .009) and fewer infants required sedation (35% vs 100%, P = .023). There was no difference in the rate of invasive mechanical ventilation and no major adverse events were observed. Another pediatric study in Spain enrolled infants less than three months of age admitted to the PICU with bronchiolitis.³ Sixteen patients were randomized to receive CPAP via a helmet or nasal prongs for the first hour then crossed over to the other group for another hour (helmet then nasal prongs or nasal prongs then helmet). Modified Wood's Clinical Asthma Score (M-WCAS) was measured at 30 minute intervals and failure was defined as the need for further respiratory support. CPAP significantly reduced respiratory distress in both groups and the failure rate was similar in both groups demonstrating CPAP delivered by nasal prongs and CPAP delivered by helmet are similar in terms of efficacy in young infants with acute bronchiolitis. Prior clinical trials have demonstrated efficacy in adults with acute respiratory distress syndrome, superior tolerance and improved respiratory scores compared to nasal/facial CPAP in infants, and no major safety concerns were identified with the use of helmet CPAP. We propose a prospective pilot study to (1) determine if infants and pediatric patients requiring CPAP in the PICU will tolerate helmet CPAP for at least four hours and (2) measure changes in the respiratory rate, oxygen saturation, heart rate and blood pressure over four hours. If helmet CPAP is found to be well tolerated in this small cohort, we will move forward with a larger study.

Study Design:

Prospective, non-randomized, single arm, interventional study.

Inclusion Criteria:

23AUGUST2021

1 month to 5 years of age (inclusive) admitted to the PICU with community acquired pneumonia or bronchiolitis, having been stable on nasal or facemask CPAP for at least two hours, and parental informed consent.

Exclusion Criteria:

Age less than 1 month or greater than 5 years, positive for COVID19, need for invasive mechanical ventilation or higher levels of non-invasive ventilation such as bi-level positive airway pressure (BPAP), unresponsiveness (GCS 8 or less), hypotension as defined as a systolic blood pressure less than 5th percentile for age, existing head or neck trauma, known or suspected air leak syndrome (pneumothorax, pneumomediastinum, sub-cutaneous emphysema), known or suspected increased cranial pressure, non-English speaking parent.

Methods:

Convenience sampling will be used to enroll 30 patients admitted to the Pediatric Intensive Care Unit (PICU) already receiving CPAP through a facemask or nasal prongs or mask for at least two hours. All patients will be transitioned to the Vyatil nonpowered oxygen tent system (Rochester, NY) by trained respiratory therapists per the manufacturer's instructions: patient's neck circumference will be measured with a soft tape measure to ensure appropriate sizing. The helmet will be connected to at least 30 liters per minute of high flow medical air with an oxygen blender. The expiratory limb will be attached to the PEEP valve (initially set at 5 centimeters of water pressure) connected to a HEPA filter to prevent any viral particles from being released into the environment. A disposable manometer will be used to measure the pressure within the helmet. Once the flow to the helmet interface is on, the helmet will be sealed and secured with the system's arm straps.

Vital signs will be recorded hourly per standard PICU care (respiratory rate, pulse oximetry, pulse, blood pressure) along with transcutaneous carbon dioxide (CO₂). The presence of adverse events (aspiration pneumonia, skin breakdown, hypotension, eye irritation, gastric distension, other) will be recorded prospectively along with total time on helmet CPAP, reason for discontinuation (patient improved, escalation of respiratory support/death, or patient not tolerating), and clinical outcome (discharged home, transferred out of PICU, intubated or death). Laboratory data (Respiratory viral panel, blood gas, complete blood count, C-reactive protein) and chest radiograph results will be recorded if obtained by the treating healthcare provider.

Primary Outcome Measure: Percentage of patients that tolerate helmet CPAP for at least four hours. Tolerance is defined as the successful application and maintenance of helmet CPAP without any unplanned, prolonged (>5 minutes) removals or disruptions. We hypothesize that at least 80% of the patients will tolerate the helmet CPAP interface for four hours.

Secondary Measures: Change in vital signs (respiratory rate, oxygen saturation, heart rate, and systolic blood pressure) over four hours. We hypothesize that vital signs will improve or remain stable throughout the application of helmet CPAP as compared to pre-helmet CPAP.

Statistical Plans:

We will present median values of vital signs longitudinally, median duration of helmet CPAP in hours, and reasons for discontinuation along with clinical outcomes and laboratory testing and imaging if available.

Study Procedures:

Convenience sampling will be used to enroll 30 patients admitted to the Pediatric Intensive Care Unit (PICU) already receiving CPAP through a facemask or nasal prongs or mask for at least two hours. All patients will be transitioned to the Vyatil nonpowered oxygen tent system (Rochester, NY) by trained respiratory therapists per the manufacturer's instructions: patient's neck circumference will be measured with a soft tape measure to ensure appropriate sizing. The helmet will be connected to at least 30 liters per minute of high flow medical air with an oxygen blender. The expiratory limb will be attached to the PEEP valve (initially set at 5 centimeters of water pressure) connected to a HEPA filter to prevent any viral particles from being released into the environment. A disposable manometer will be used to measure the pressure within the helmet. Once the flow to the helmet interface is on, the helmet will be sealed and secured with the system's arm straps.

Vital signs will be recorded hourly per standard PICU care (respiratory rate, pulse oximetry, pulse, blood pressure) along with transcutaneous carbon dioxide (CO₂). The presence of adverse events (aspiration pneumonia, skin breakdown, hypotension, eye irritation, gastric distension, other) will be recorded prospectively along with total time on helmet CPAP, reason for discontinuation (patient improved, escalation of respiratory support/death, or patient not tolerating), and clinical outcome (discharged home, transferred out of PICU, intubated or death). Laboratory data (Respiratory viral panel, blood gas, complete blood count, C-reactive protein) and chest radiograph results will be recorded if obtained by the treating healthcare provider.

Inclusion Criteria: 1 month to 5 years of age (inclusive) admitted to the PICU with community acquired pneumonia or bronchiolitis, having been stable on nasal or facemask CPAP for at least two hours, and parental informed consent.

Exclusion Criteria: Age less than 1 month or greater than 5 years, positive for COVID-19, need for invasive mechanical ventilation or higher levels of non-invasive ventilation such as bi-level positive airway pressure (BPAP), unresponsiveness (GCS 8 or less), hypotension as defined as a systolic blood pressure less than 5th percentile for age, existing head or neck trauma, known or suspected air leak syndrome (pneumothorax, pneumomediastinum, subcutaneous emphysema), known or suspected increased intracranial pressure, non-English speaking parent.

Potential Risks:

Skin irritation around the neck, too much air pressure to the lungs causing discomfort and lowering blood pressure are potential risk of using helmet CPAP. There is a small risk of breach of confidentiality.

Potential Benefits:

Helmet CPAP may provide a better seal thus delivering CPAP more effectively leading to improved respiratory status. Helmet CPAP may be more comfortable than face mask, nasal mask or nasal prong CPAP.

Alternatives:

23AUGUST2021

The alternative is not to participate and continue receiving CPAP through a facemask, nasal mask or nasal prongs.

Data Security & Monitoring:

The PI is an experienced pediatric critical care physician who will review all adverse and unanticipated events.

References

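### Convenience sampling may let expected tolerance influence who is enrolled, and in a single-arm pilot any such selection passes straight into the primary percentage

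*Protocol*

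**What the plan says.** The Protocol gives the sampling method twice in the same words, under Methods and under Study Procedures: "Convenience sampling will be used to enroll 30 patients admitted to the Pediatric Intensive Care Unit (PICU"). Neither section says who approaches families, at what times or in what order, and the Protocol asks for no record of eligible children who are not enrolled.

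Four other statements bear on the point:

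- Study Design: "Prospective, non-randomized, single arm, interventional study".
- Inclusion Criteria: the child must qualify by "having been stable on nasal or facemask CPAP for at least two hours, and parental informed consent".
- Primary Outcome Measure: "Percentage of patients that tolerate helmet CPAP for at least four hours", with the expectation "We hypothesize that at least 80% of the patients will tolerate the helmet CPAP interface for four hours".
- Study Purpose and Rationale: the aim is to "determine if infants and pediatric patients requiring CPAP in the PICU will tolerate helmet CPAP for at least four hours", and the result has a use: "If helmet CPAP is found to be well tolerated in this small cohort, we will move forward with a larger study".

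**The concern.** The primary outcome depends largely on behaviour: whether a young child keeps a helmet on for four hours without an unplanned removal or disruption of more than five minutes. The rationale itself notes that young children comply less well than adults with keeping an interface in place. By the time a child is eligible, at least two hours on another interface have shown how that child copes. A plausible predictor of the primary outcome is therefore visible before anyone is approached, and convenience sampling sets no rule to stop it from influencing who is enrolled.

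In a randomised comparison such selection would affect both arms. Here there is one arm, so it moves the reported percentage directly. At stake is whether that percentage describes children who need CPAP in the PICU, which is the stated target, or only those who happened to be enrolled. The case for a larger study, and any tolerance rate assumed in planning it, would rest on that figure. A statistical analysis plan could not repair this afterwards, because the selection takes place at enrolment.

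**Working it through.** **No plan figure to reproduce.** The Protocol attaches no null rate, power or precision target to the 30 patients. The only arithmetic it supports is 0.80 × 30 = 24.

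**Inputs from the Protocol.** n = 30, one arm, hypothesised tolerance of at least 80%.

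**Assumed inputs, for illustration only.**
- Half of eligible children are calm and half are not.
- Calm children tolerate the helmet at rate a, the others at rate b, with a true overall rate of (a + b)/2 = 70%.
- Calm children are k times as likely to be enrolled as the others.
- 24 of 30 serves as a benchmark for a good result.

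**Formulas.** The expected rate among enrolled children is q = (k·a + b)/(k + 1). The chance of reaching the benchmark is P(X ≥ 24) with X ~ Binomial(30, q).

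**No selection (k = 1).** q = 70% and P = 16.0%.

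**Calmer children favoured**

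| k | q, a = 85%, b = 55% | P(X ≥ 24) | q, a = 75%, b = 65% | P(X ≥ 24) |
|---|---|---|---|---|
| 2 | (2 × 0.85 + 0.55)/3 = 75.0% | 34.8% | (2 × 0.75 + 0.65)/3 = 71.7% | 21.2% |
| 3 | (3 × 0.85 + 0.55)/4 = 77.5% | 47.3% | (3 × 0.75 + 0.65)/4 = 72.5% | 24.2% |
| 4 | (4 × 0.85 + 0.55)/5 = 79.0% | 55.3% | (4 × 0.75 + 0.65)/5 = 73.0% | 26.2% |

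**Children who cope poorly favoured.** If the other children are enrolled twice as often, q = (0.85 + 2 × 0.55)/3 = 65.0% and P = 5.9% under the wide contrast. Under the narrow one, q = (0.75 + 2 × 0.65)/3 = 68.3% and P = 11.7%.

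**What a confidence interval would show.** For 24 of 30 the exact 95% interval is 61.4% to 92.3%. It covers sampling error only and gives no sign of selection in either direction.

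**The case against.** The strongest reply is that this is an openly stated choice in a study that calls itself a pilot. Convenience sampling is common in pilots, and nothing in the Protocol is contradicted. That stands: this is a design weakness that can be improved cheaply, not an error.

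A reader might infer that staff will pick calm children and that the tolerance rate will therefore be too high. The Protocol supports neither step. It does not say who selects. Convenience may mean no more than that a trained therapist, a helmet or a parent was available, which need not track temperament. The bias could also run the other way: the helmet is presented as an alternative to interfaces that young children keep on poorly, so clinicians might offer it first to those struggling with a mask. The requirement of stability on CPAP limits that and may also narrow the room for selection generally.

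The illustration is fragile too. No document supports the 70% starting rate, the contrasts or the enrolment ratios. The infant trial cited in the rationale reports 17% failure from intolerance with the helmet (n = 17), which suggests about 83%, although its definition and age range may differ. At a true 83% the chance of at least 24 of 30 is already 76% without any selection.

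These objections limit what can be said about direction and size. They do not remove the opening for selection, and without a record of eligible children nobody could tell afterwards which way it ran.

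**Conclusion.** The point holds as a cheap improvement. The Protocol fixes a sampling method that may let expected tolerance influence enrolment, and the single-arm design has nothing to offset it in the primary percentage. The documents do not establish the direction or the size of any bias.

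Under the assumed inputs, a two- to fourfold preference for calmer children shifts the expected rate by 5 to 9 percentage points with the wide contrast and by about 2 to 3 points with the narrow one. How much that matters against 24 of 30 depends on the true rate.

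Two stronger conclusions are not supported. The first is that the pilot will overstate tolerance and that unselected patients will fall short of its rate. The second is that 80% is the cut-off for proceeding: the Protocol ties the larger study to good tolerance without a number and gives 80% only as a hypothesis.

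**What to change.** Under both Methods and Study Procedures, replace convenience sampling with a rule such as: every eligible child present during pre-declared hours, when the existing study team (a trained respiratory therapist and someone able to obtain consent) is already available, will be approached consecutively until 30 are enrolled.

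Keep a short de-identified log with one line per eligible child: age, approached or not, consented or not, and the reason if not enrolled. Report these counts beside the primary percentage. If consecutive approach proves impractical, the log alone would still let readers judge how selective enrolment was.

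Sample size, eligibility, device and treatment stay as they are. The cost is some logging and consent work, and possibly slower accrual. The documents give no staffing details, so it cannot be claimed that the change costs no staff time. Refusal of consent remains a source of selection, but the log would make it visible.

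### Does the 80% tolerance hypothesis demand more than 30 children can show?

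*Protocol*

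**What the plan says.** Under Primary Outcome Measure the Protocol names the endpoint, "Percentage of patients that tolerate helmet CPAP for at least four hours", and then the expectation: "We hypothesize that at least 80% of the patients will tolerate the helmet CPAP interface for four hours".

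Study Design describes the trial as "Prospective, non-randomized, single arm, interventional study", and Methods fixes the size: "Convenience sampling will be used to enroll 30 patients". No alpha, power, target precision or other basis for 30 is given.

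The Statistical Plans section is descriptive: "We will present median values of vital signs longitudinally, median duration of helmet CPAP in hours, and reasons for discontinuation along with clinical outcomes", together with laboratory and imaging results where available. It does not mention the primary percentage.

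The decision that follows is in Study Purpose and Rationale: "If helmet CPAP is found to be well tolerated in this small cohort, we will move forward with a larger study". No number is attached to it. The same section gives the only paediatric tolerance figure, from a trial with 17 infants in the helmet group: "Helmet CPAP had a lower treatment failure rate due to intolerance (17% vs 54%, P = .009" in favour of the helmet over the facial mask.

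**The concern.** A numeric, directional hypothesis, a fixed sample size and a go decision all appear in the Protocol, and nothing joins them. A reader naturally fills the gap: 24 or more of 30 tolerate the helmet, so the hypothesis is confirmed and the larger study goes ahead. Under that reading a point estimate would carry a claim of at least 80% that 30 children can rarely support. A helmet somewhat below 80% could pass, and one exactly at 80% would often fail. The primary conclusion and the one decision the pilot feeds would then rest on weak ground. That the Statistical Plans leave out the primary percentage strengthens the impression.

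**Working it through.** **Inputs.** From the Protocol: n = 30 (Methods), threshold 80% (Primary Outcome Measure), intolerance failure 17% in the cited infant trial (Study Purpose and Rationale), so about 100% − 17% = 83% tolerating. The Protocol states no alpha or sidedness, so both usual choices are shown as assumptions. It gives no sample-size calculation, so there is no planned figure to reproduce.

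**Step 1: what an observed count says about the true rate.** The exact (Clopper-Pearson) limits for x of n are the 2.5% quantile of Beta(x, n − x + 1) and the 97.5% quantile of Beta(x + 1, n − x). The one-sided 95% lower limit uses the 5% quantile of the first distribution.

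| Tolerating | Observed | Two-sided 95% interval | One-sided 95% lower limit |
|---|---|---|---|
| 24/30 | 80.0% | 61.4% to 92.3% | 64.3% |
| 27/30 | 90.0% | 73.5% to 97.9% | 76.1% |
| 28/30 | 93.3% | 77.9% to 99.2% | 80.5% |
| 29/30 | 96.7% | 82.8% to 99.9% | 85.1% |
| 30/30 | 100% | 88.4% to 100% | 90.5% |

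Check by direct summation at a true rate of 0.80:

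- P(X ≥ 29) = 30 × 0.8²⁹ × 0.2 + 0.8³⁰ = 0.0105
- P(X ≥ 28) = 435 × 0.8²⁸ × 0.2² + 0.0105 = 0.0442

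So 29 are needed at one-sided 2.5% (the two-sided 95% interval), and 28 are enough at one-sided 5%. A two-sided 95% Jeffreys interval is also satisfied by 28 (lower limit 80.3%). No single count is the requirement unless an error rate and a method are chosen, and the Protocol chooses neither.

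**Step 2: how often each possible rule would be met.** P(X ≥ k | p) for n = 30:

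| True rate | 24 or more | 28 or more | 29 or more |
|---|---|---|---|
| 70% | 0.1595 | 0.0021 | 0.0003 |
| 75% | 0.3481 | 0.0106 | 0.0020 |
| 80% | 0.6070 | 0.0442 | 0.0105 |
| 83% | 0.7610 | 0.0949 | 0.0267 |
| 90% | 0.9742 | 0.4114 | 0.1837 |

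If the rule were an observed 80%, a helmet with a true rate of 70% would pass about 16% of the time. One at 75% would pass about 35% of the time, and one at exactly 80% would miss in 1 − 0.607 = 39% of trials.

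**Step 3: is any of these rules in the Protocol?** Set the relevant sections beside the rules:

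- *Primary Outcome Measure* states what is expected. It gives no criterion for confirming it and does not say that a population rate above 80% will be demonstrated.
- *Statistical Plans* contains no test of any endpoint. Its descriptive character fits a pilot.
- *Study Purpose and Rationale* makes the larger study depend on tolerance in the small cohort itself and does not mention 80%.

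The 24-of-30 rule and the 28- or 29-of-30 rules are therefore all supplied by the reader. Step 2 describes rules the trial could have adopted, not one it has adopted. Read as an expected cohort result, 80% sits just under the 83% of the cited trial, so the hypothesis agrees with the Protocol's own evidence.

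**The case for a change.** The best argument for the concern is that threshold, sample size and go criterion are protocol-level choices. A statistical analysis plan can add an interval, but it cannot make 30 children sufficient to show at least 80% when the true rate is about 83%: the chance of 28 or more is then only 9.5%, and of 29 or more 2.7%. If the 80% is an observed benchmark instead, it misclassifies fairly often near the threshold. The Protocol does not say which reading applies, so well tolerated could be defined after the data are seen.

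Part of this stands. The arithmetic is correct, 30 is not justified, and the go criterion has no number. But low precision is an error only against a stated aim of precision, power or proof, and the Protocol states none. Error rates of 16% at a true 70% and 35% at a true 75% are modest for a pilot whose consequence is further study. The natural remedy also shows how little is at stake: a rule of proceeding on 24 or more of 30, reported with an exact interval, has exactly the operating characteristics complained of. The report would be clearer, but the decision would be the same. The remaining gap, no written interval or success rule for one proportion, is detail commonly placed in a statistical analysis plan, so its absence from the Protocol alone is no finding.

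**Conclusion.** The concern does not hold. The Protocol gives 80% as an expectation for a descriptive, single-arm pilot. It makes no inferential claim that 30 children fail to support, and it does not tie the larger study to that figure. The calculations are sound: 24/30 has an exact 95% interval of 61.4% to 92.3%, and excluding rates below 80% takes 29/30 at two-sided 95% or 28/30 at one-sided 5%. They measure the trial against a standard it does not set.

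This rests on two assumptions: that the hypothesis is read as an expected cohort result, which the pilot design, convenience sampling and descriptive analyses support, and that interval and decision details may sit in a statistical analysis plan that is not shown. If the results were later reported as proof that at least 80% of such children tolerate the helmet on the strength of 24/30, that report would be open to criticism. The Protocol as written does not commit to it.

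### Group medians over time do not answer a before-after hypothesis: report within-child change, the number of children who worsen, and the pre-helmet hours

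*Protocol*

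**What the plan says.** Study Design declares a "Prospective, non-randomized, single arm, interventional study". Inclusion Criteria admit children "having been stable on nasal or facemask CPAP for at least two hours". Methods plan the sample as follows: "Convenience sampling will be used to enroll 30 patients". On measurement they state: "Vital signs will be recorded hourly per standard PICU care".

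The secondary measure is "Change in vital signs (respiratory rate, oxygen saturation, heart rate, and systolic blood pressure) over four hours", with the hypothesis "We hypothesize that vital signs will improve or remain stable throughout the application of helmet CPAP as compared to pre-helmet CPAP". For these data, Statistical Plans state only this: "We will present median values of vital signs longitudinally".

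The Protocol does not say which pre-helmet reading or window is the comparator. It does not say that readings from the two qualifying hours are collected for the study. It plans no test or interval for vital signs and states no causal conclusion about them. Only the Protocol is at hand; a separate SAP may exist.

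**The concern.** The hypothesis and the stated analysis do not match. The hypothesis asks how children on the helmet compare with their own state before it. A series of group medians describes the middle of the group at each hour and pairs no child with that child's own earlier value. It can look steady while a substantial minority deteriorate, which is what a check for stability after a change of interface should reveal.

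The hypothesis is also easy to meet. In a single arm, a child who is unaffected by the helmet and stable meets it, and so does a child who is unaffected and recovering. If the display begins at the switch, nothing in it shows whether a fall in respiratory or heart rate had already begun.

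At stake is how one of the two numbered aims in the Background will be read. Potential Benefits names better respiratory status as a possible gain, so a falling median may well be taken as a sign of one.

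**Working it through.** The Protocol gives no standard deviation, margin, error rate or effect size for vital signs, so there is no figure of its own to reproduce. From the Protocol: n = 30, hourly readings, at least two qualifying hours, four hours of follow-up. Every drift and SD below is an assumption.

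**1. What a group median can hide.** With 30 values, the median is the mean of the 15th and 16th in rank. Ranks 17 to 30 are 14 children. If respiratory rate rises by any amount in all 14 and is unchanged in the others, the median does not move: 14/30 = 47%. This is a bound on what can go unseen, not a forecast. The median of paired changes has the same blind spot, since 14 of 30 changes can be adverse with the median change at zero. A count of children who worsen is therefore needed as well.

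**2. What drift alone does.** Assume no helmet effect and a steady natural fall in respiratory rate of d breaths/min per hour, with the last pre-helmet reading at the switch. The apparent change at hour 4 is 4 × d.

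| d (assumed) | Apparent fall at 4 h | Hypothesis met? |
|---|---|---|
| 0 | 0 | yes (stable) |
| 0.5 | 2 | yes |
| 1 | 4 | yes |
| 1.5 | 6 | yes |

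**3. Can the pre-helmet hours remove the drift?** They can show it, but hardly estimate it. Let s be the within-child residual SD, with independent errors.

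- Simple change from one reading: SE = s√(2/30) = 0.26 s.
- Change from each child's own pre-helmet line, extrapolated to hour 4, with readings at −2, −1 and 0 h (mean time −1, Sxx = 2): SE = s√[(1 + 1/3 + 5²/2)/30] = s√(13.83/30) = 0.68 s. The ratio to the simple change is 2.63.
- Slope over hours 1 to 4 (Sxx = 5) minus the pre-helmet slope, assuming an SD of 8 for the change, so s² = 8²/2 = 32. With three pre-helmet readings the variance is 32(1/5 + 1/2) = 22.4, and the 95% half-width is 2.045 × √(22.4/30) = 1.8 breaths/min per hour. With two readings (Sxx = 0.5) the variance is 32(1/5 + 2) = 70.4, and the half-width is 3.1.

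Both half-widths exceed the largest drift in the table. A formal before-and-after slope contrast would say almost nothing at this size.

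**4. Which baseline?** Averaging several pre-helmet readings looks attractive because it reduces noise. Under drift it also moves the baseline back in time. With d = 1, the average of −2, −1 and 0 h is centred at −1 h, so the spurious change at hour 4 becomes 4 − (−1) = 5 instead of 4. With two readings (−1 and 0 h) it is 4.5. The last reading before the switch carries the least drift.

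**The case against.** The strongest reply is that this is an openly declared single-arm pilot, that the analysis is descriptive, and that the hypothesis reads most naturally as a check that children do not deteriorate. Entry requires stability on CPAP, which limits a steep prior trend and regression to the mean. The exact baseline window is the kind of detail an SAP may fix. Most of this stands, and it sets the weight of the point. It does not answer the mismatch between a before-after hypothesis and unpaired group medians, both of which the Protocol itself states. Stability for two hours does not rule out recovery in the next four.

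Four stronger readings are tempting, and the documents do not support them:

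- A reader might infer that pre-helmet data are not used at all. The hypothesis names pre-helmet CPAP as its comparator, and the longitudinal medians could include those hours. The Protocol is silent on which readings and how.
- A reader might infer that natural recovery will be reported as a helmet effect. No efficacy conclusion is planned, and that these children are recovering is an inference. What can be said is that the two cannot be told apart.
- A reader might calculate how often a confidence interval would wrongly exclude zero. The Protocol plans no such interval or test, so the figure would describe a different analysis.
- A reader might infer that this outcome drives the next study. The Background ties that step to tolerance: "If helmet CPAP is found to be well tolerated in this small cohort, we will move forward with a larger study".

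**Conclusion.** The point holds as a minor one. The stated analysis does not report the within-child change that the hypothesis is about. It can leave up to 14 of 30 worsening children unseen even when every other child is unchanged. Unless the pre-helmet hours are displayed, it also gives no view of the earlier course. The 14 of 30 follows from the sample size alone. The drift table and slope half-widths rest on assumed drift, an assumed SD of 8 and independent errors, and serve only to show direction and scale. No reporting change removes the confounding of time with the helmet in a single arm; better reporting makes it visible and keeps the conclusion within what the data can bear.

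**What to change.** In Secondary Measures and Statistical Plans:

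1. Abstract the hourly vital signs already charted in the two qualifying hours before the switch.
2. Take the last pre-helmet reading as baseline and report each child's paired change at hours 1 to 4, as a median change with an interval, alongside the group medians. Do not average the baseline.
3. Display values from −2 h to +4 h as description only, without a formal slope comparison.
4. Report how many children worsen on each vital sign. The investigators should set the direction and size that count as worsening before the data are seen. If any adverse movement counted, symmetric measurement noise alone would place about half the children in that group.
5. State that changes are descriptive and are not attributed to the helmet.

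The cost is two or three extra chart rows per child and a few lines of text. No new measurement is needed, because standard hourly charting should already hold the readings.
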